a culturally adapted technology-delivered FBCO intervention for L/H families in rural Nebraska. Applying an iterative collaborative process, we will use a mixed-methods approach to culturally adapt FC to better fit the rural L/H community profile. A Community Workgroup facilitated by our rural partner organizations in Nebraska with a high population of L/H residents and theory-and data-driven approach using structured community input adaptation process will be conducted to develop and evaluate the relevance (ecological validity and equivalence), acceptability, and usability of all the adaptations made. We hypothesize that this process will lead to a program that is relevant, acceptable, and usable by L/H families in rural communities.

Aim 2: To evaluate the feasibility and preliminary effectiveness of a technology-delivered FBCO intervention for L/H families in rural Nebraska using RE-AIM and i-PARIHS. We will randomly assign participants to either FC (n=29) or an enhanced standard-care (SC) group (n=29) and determine overall study reach, preliminary effectiveness in reducing child BMI z-scores, potential for program adoption, implementation, and sustainability through local health departments (RE-AIM outcomes). SC participants will receive a workbook. FC participants will receive a workbook, 2 in person group sessions followed by 10 IVR calls over a period of 6 months. We hypothesize that a culturally adapted FC program will lead to a higher engagement (reach, retention and completion), significant higher proportion of L/H children reducing their BMIz scores at 6 months when compared to SC group, align (social validity) with health department perceptions of i-PARIHS constructs (Innovation, context, recipient characteristics), and that FC participants will view the intervention positively (i.e. relative advantage, observability, trialability, complexity, compatibility).

3. Background and Rationale

Describe the background of the study. Include a critical evaluation of existing knowledge, and specifically identify the information gaps that the project is intended to fill.

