
relevance (aim 1 measures) and acceptability identified in exit survey/interviews to determine whether intervention is appropriate for further testing. Qualitative Analysis. Qualitative interviews and FGs will be recorded and transcribed in English or Spanish. The PI, with assistance from [name] and [name] will construct the interview codebook, with inductive codes added iteratively by in-depth reading of transcriptions until saturation is achieved. Transcripts will be double-coded in NVivo by [name], [name] and the PI. Inter-coder reliability using Cohens kappa (goal > 0.80) will be assessed. The research team has extensive experience conducting qualitative investigation^{20,22,26,51,58,62,67}, possesses local linguistic expertise (Drs. [name] and [name], speak Spanish), and will be aided by bilingual (English-Spanish) CHW staff. Statistical Analysis: The association of the intervention with the primary outcome of proportion of children reducing BMI z-scores will be tested using a chi-square test. The degree of association will be summarized using the odds ratio. If the assumptions of the chi-square test are violated, Fishers exact test will be utilized. Potential gender, and acculturation scores (external and familial language use, and social relations) differences will be explored via stratification. Comparisons between groups within gender will be done using Fishers exact test. Secondary aims outcomes include parent BMI, waist, PA, sweet beverages intake and eating behaviors, home environment changes and quality of life. The quantitative outcomes will be summarized using means and standard deviations or medians and inter-quartile ranges, as appropriate. If categorized, outcomes will be summarized using counts and percentages. Between group differences at 6-month will be capture using ANCOVA with the baseline measure as the covariate. If the ANCOVA assumptions are violated, a t-test (or if indicated, Wilcoxon's sum rank test) between group change scores (6-month baseline measure) will be used. Potential parental engagement (% of reach, retention and completion) and acculturation scores (language and media use, and social ethnic relations) differences will be explored via stratification. Comparisons between groups will be done using Fishers exact test. Significance level is 0.05.

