As we have done in prior studies, a manual of procedures will be developed during the initial study start-up period that explicitly describes the specific procedures related to the delivery of focus groups, data collection and safety, and quality assurance for all study stages.

Implementation study measures:	Variables	Approx. minutes	Baseline	6-Month
Child				
Weight	Raw units (Kg), percentage, BMIz-scores	3 min	x	x
Height	Height (cm).	3 min	x	x
Waist Circumference	Waist Circumference (cm)	3 min	x	x
Blood pressure	Systolic and Diastolic pressure (mmHg)	5 min	x	x
Physical Activity (Godin-Child Questionnaire99)	Time of vigorous, moderate, mild exercise. Score and category (active/insufficient)	3 min	x	x
Nutrition (BRFSS fruits and vegetables100 and BEVQ101)	Fruit and vegetables servings and sugar sweetened beverage consumption	5 min	x	x
Quality of Life (PEDS-QL103)	Physical Health and Psychosocial Health Score, Sum Score	5 min	x	x
Health Literacy (New Signal Vital-NVS106)	Health literacy and Numeracy, Sum score of and categorized (limited/adequate)	3 min	x	x

Acculturation (Short Acculturation Scale for Hispanic Youth104)	External language use, familial language use, social relations scores, total score, rank (low/high)	3 min	x	x
Parent				
Weight	Raw units (Kg), percentage, BMI.	3 min	x	x
Height	Height in cm.	3 min	x	x
Waist Circumference	Waist Circumference in cm.	5 min	x	x
Blood Pressure	Systolic and Diastolic pressure (mmHg)	5 min	x	x
Physical Activity (Godin Leisure Time Exercise Questionnaire98)	Time of vigorous, moderate, or mild exercise. Sedentary Behaviors. Score and category (active /insufficient).	3 min	x	x
Nutrition (BRFSS fruits and vegetables100 and BEVQ101)	Fruit and vegetables servings and sugar sweetened beverage consumption.	5 min	x	x
Health Literacy (New Signal Vital-NVS106)	Health literacy and Numeracy, Sum score of and categorized (limited/adequate)	5 min	x	x
Quality of Life (BRFSS Healthy Days102)	General health status Number of Healthy Days	3 min	x	x
Home Environment (Comprehensive Home Environment Survey107)	Food, Physical activity, and Media home environment scores and total score.	10 min	x	x
Acculturation (Bidimensional Acculturation Scale105)	Language and media use, and social-ethnic relations scores, total score and rank (low/high).	3 min	x	x
Qualitative interview on process and program feedback	Feedback and Satisfaction with intervention components	20 min		x

- *all measures are available in both English and Spanish versions*

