Statistical Analysis: Descriptive, parametric, and non-parametric statistical methods will be used to compare continuous and categorical variables among the intervention groups at baseline. Data will be examined for the presence of outliers, violations of normality (for those continuous variables) and missing data. Major violations of normality will be corrected with an appropriate transformation procedure or non-parametric methods . Multi-level mixed effect models will be employed to control errors of non-independence, heteroskedasticity caused by parent-child dyad heterogeneity, and potential covariates to control to detect the BMI z-score reduction differences between the two conditions. In its simplest form, the model generally can be shown as:

$$BMIZscore_{it} = \mu + \alpha_i + X_{ijt} \beta + W_i \sigma + TT_t + \theta d_i + T_t + v_{it}$$

All measures are obtained for 3 time periods: baseline, 6, and 12 months. The dependent variable is BMIZ score for participant i at time point t . The unobserved participant-level heterogeneity that is not time dependent is represented by α_i , is allowed to vary by parent-child-dyads and to be a random variable. The X_{it} are time-period-level covariates and the W_i are participant-level covariates. The model also contains treatment group indicators d_i , and

time period indicators T_t . Relative treatment effect between conditions will be captured by coefficient θ and is the variable of interest. Sensitivity analysis will be conducted to examine the robustness of the mixed effect model across different random-effect distribution specifications (e.g., normal, finite mixture of normal etc.). Additional outcomes (e.g., parent BMI, waist circumference, PA, sweet beverages intake and eating behaviors, acculturation, home environment changes and quality of life) will be analyzed using ANCOVA with the baseline measure as the covariate. If the ANCOVA assumptions are violated, a t-test (or if indicated, Wilcoxon's sum rank test) between group change scores (6 or 12 month measure and baseline measure) will be used. Significance level for all tests is 0.05. Analyses will be performed using R 3.6 (R Core Team).

F. Does this study involve the collection of blood, urine, saliva or other human biological material (HBM)?

No

DRUGS, BIOLOGIC DRUGS AND DEVICES

13. Drugs and Biologic Drugs

1. Does this research involve the use of drugs or biologics?

No

14. Devices

1. Does this research involve a medical device(s)?

No

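### The primary 6-month comparison of children reducing BMI z-score ignores the baseline BMI z-score, leaving a small trial exposed to chance baseline imbalance that a pre-specified covariate would largely remove

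*Combined protocol and SAP*

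**What the plan says.** The Aim 2 hypothesis (section 2) is a "significant higher proportion of L/H children reducing their BMIz scores at 6 months when compared to SC group". The Statistical Analysis paragraph of section 12.B matches it: the "primary outcome of proportion of children reducing BMI z-scores will be tested using a chi-square test", the association is summarised by an odds ratio, and "If the assumptions of the chi-square test are violated, Fishers exact test will be utilized". No baseline covariate enters either test. Gender and acculturation are explored by stratification only.

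For the quantitative secondary outcomes the same paragraph says "Between group differences at 6-month will be capture using ANCOVA with the baseline measure as the covariate". The fallback drops the covariate: "If the ANCOVA assumptions are violated, a t-test (or if indicated, Wilcoxon's sum rank test) between group change scores".

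The measures table in section 12.B lists child weight as "Raw units (Kg), percentage, BMIz-scores", at baseline and at 6 months, so the covariate is already collected. Sections 12.B and 12.C describe randomisation from a random-numbers table and mention no stratification.

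Section 12.E gives a second analysis, of continuous BMI z-score: "Multi-level mixed effect models will be employed to control errors of non-independence". It adds: "Relative treatment effect between conditions will be captured by coefficient θ and is the variable of interest". It does not call this model primary and does not list its covariates, and baseline enters as one of the modelled time points. Table 1 in section 12.E names the primary outcome simply as BMI z-score.

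**The concern.** Defining the outcome as a fall from the child's own baseline does not make it independent of that baseline. Children enter on a cut-off at the 85th percentile (section 9), and after selection on a high reading the more extreme values can be expected to drift down more. If so, an arm that starts higher by chance will show more children reducing BMI z-score without any treatment effect, and a 2x2 table cannot separate the two.

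At stake is the credibility of the headline result in a trial too small to rely on randomisation alone for balance. A nominally significant difference, or its absence, could partly reflect where the arms started. The analysis named for the primary outcome also gets less protection than the default analysis of the quantitative secondary outcomes.

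**Working it through.** **Inputs from the documents.** Difference 0.05 and SD 0.06 for 6-month change in BMI z-score, alpha 0.05, power 80%, 23 evaluable and 29 recruited per arm (sections 12.B and 12.E).

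**Assumed, because not given.** The size r of the baseline-change correlation (0 to 0.5; a higher baseline goes with a larger fall) and the mean change in standard care (0 or -0.025).

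**1. The plan's own figure.** n per arm = 2 × (1.960 + 0.842)² × (0.06/0.05)² = 2 × 7.85 × 1.44 = 22.6, so 23. This reproduces the stated 46, for a two-sided comparison of mean change.

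**2. The same inputs on the binary scale.** With a standard-care mean change of 0, the proportions reducing are Φ(0) = 50.0% and Φ(0.05/0.06) = 79.8%. Chi-square power at 23 per arm is about 57%. With a mean change of -0.025 they are 66.2% and 89.4%, and power is about 50%.

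**3. How large a chance gap is likely.** The SE of the difference in baseline means, in baseline SDs, is √(2/23) = 0.295 with 23 per arm and √(2/29) = 0.263 with 29. The chance of a gap above 0.5 SD is 2 × [1 − Φ(0.5/0.295)] = 9.0% with 23 and 2 × [1 − Φ(0.5/0.263)] = 5.7% with 29.

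**4. What such a gap does.** A gap of 0.5 SD shifts mean change by r × 0.5 × 0.06. That is 0.009 at r = 0.3 and 0.015 at r = 0.5, or 18% and 30% of the planned 0.05. On the proportion scale near 50% the shift is about φ(0) × r × 0.5 = 0.399 × r × 0.5, which is 6 percentage points at r = 0.3 and 10 at r = 0.5. The planned difference is 29.8.

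**5. Simulation.** 23 per arm, normal change with SD 0.06. Power uses 20,000 trials per setting and the no-effect runs use 60,000. The adjusted test is a likelihood-ratio test (LRT) from logistic regression on group and continuous baseline.

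| Standard-care mean change | r | Power: chi-square | Power: adjusted LRT | No effect, gap > 0.5 SD: chi-square | No effect, gap > 0.5 SD: adjusted LRT |
|---|---|---|---|---|---|
| 0 | 0 | 57.6% | 58.9% | 5.3% | 5.4% |
| 0 | 0.3 | 57.5% | 61.5% | 7.4% | 5.2% |
| 0 | 0.45 | 56.9% | 64.1% | 11.3% | 5.8% |
| 0 | 0.5 | 56.7% | 65.7% | 11.5% | 5.9% |
| -0.025 | 0 | 49.6% | 51.0% | 5.4% | 6.5% |
| -0.025 | 0.3 | 50.7% | 53.9% | 7.9% | 6.2% |
| -0.025 | 0.45 | 49.8% | 56.0% | 10.0% | 6.1% |
| -0.025 | 0.5 | 50.3% | 58.0% | 11.1% | 6.2% |

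Over all no-effect trials the type I error is 5.0 to 5.5% for chi-square and 5.6 to 6.1% for the adjusted LRT. A smaller run of the same design gave conditional false-positive rates of about 8% at r = 0.3 and 11 to 14% at r of 0.45 to 0.5, against 6 to 7% adjusted. The summary ranges cover both runs.

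**6. The choice of test matters.** At r = 0 the LRT still appears to gain about 1.3 points, although baseline explains nothing. That part is slight anti-conservatism, not precision. A Wald test of the same adjusted coefficient loses about 1 to 2 points against chi-square for r up to 0.2 when standard-care change is 0. When standard-care change is -0.025 and cells are sparser, it falls to 36% (r = 0) and 42% (r = 0.5), against about 50% for chi-square.

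**The case against.** The strongest reply has four parts.

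- **Validity.** The chi-square test is valid under randomisation, and its type I error already averages over chance imbalance. This stands. A reader might infer that the planned test is invalid, and the figures do not support that.
- **Size.** The outcome is already change from the child's own baseline, so a typical gap matters little: 0.263 SD at r = 0.3 shifts mean change by 0.3 × 0.263 × 0.06 = 0.0047, about 9% of the planned 0.05. This also stands. A reader might infer that adjustment is free precision. The documents give no r, the gain is negligible if r is near zero, part of it is anti-conservatism, and a Wald test can lose power.
- **Section 12.E.** Its mixed model already uses baseline as a time point and allows covariates. This stands only in part. If that model were declared primary, the chi-square would no longer be the primary test. Section 12.E never declares it, and section 12.B assigns the primary outcome to the chi-square explicitly.
- **Sparse cells.** Section 12.B has Fisher's exact test for sparse tables, while logistic regression can meet separation. With 80 to 89% of intervention children reducing, only about 2 to 5 of 23 do not. This stands, and the fix must deal with it.

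It is also tempting to say that the primary outcome is the only one left unadjusted. The documents do not support that: the engagement and acculturation comparisons use Fisher's test, and the secondary ANCOVA has an unadjusted change-score fallback.

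**Conclusion.** The point holds in a limited form. The analysis named for the primary outcome omits a baseline value that the trial collects anyway, and so lacks protection in the roughly 9% of trials (23 per arm) with a baseline gap above 0.5 SD. In those trials the false-positive rate is about 8% at r = 0.3 and 10 to 14% at r of 0.45 to 0.5, against about 5 to 7% with the adjusted likelihood-ratio test. The power gain is modest: about 1 to 4 points for r up to 0.3 and about 6 to 9 points at r of 0.45 to 0.5. All of this rests on an assumed r, an assumed standard-care change and normally distributed change.

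A reader might also infer that adjustment brings the trial back to its planned 80% power. It does not. Even at r = 0.5 the adjusted binary test reaches only about 58 to 66%. The larger loss comes from dichotomising an endpoint that was sized on continuous change, which is a separate issue.

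**What to change.** Pre-specify continuous baseline BMI z-score as a covariate in the primary 6-month comparison, and state in sections 12.B and 12.E which analysis is primary and how it relates to the mixed model.

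If the endpoint stays binary:

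- use logistic regression on group and continuous baseline BMI z-score, tested by likelihood ratio and not by Wald;
- report the covariate-standardised risk difference with its 95% CI, alongside the conditional odds ratio;
- name a fallback for sparse cells or separation, for example Firth-penalised logistic regression;
- keep the chi-square or Fisher test as a supportive analysis.

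The cost is analysis-plan wording, with no new data. There are two small downsides. The odds ratio becomes conditional on baseline, which is why the standardised risk difference should be reported with it. And the benefit is negligible if baseline and change turn out to be nearly uncorrelated.

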Specific Aim 2: To evaluate the feasibility and preliminary effectiveness of a technology-delivered FBCO intervention for L/H families in rural Nebraska using RE-AIM and i-PARIHS. We will randomly assign participants to either the intervention or an enhanced standard care group (Figure 3). Sample Size Calculation. Sample size is based on the comparison of changes in BMI z-scores achieved by participants in FC-IVR with those achieved by participants in FC-workbook condition at 6 months post randomization²⁰. A total of 46 (23 per group) parent-child dyads achieves 80% power (alpha 0.05) to detect a significant difference between SC and IVR groups conditions. To account for a 25% attrition rate at 6-month we will recruit a total of 58 (29 per group) dyads. Participant Recruitment and Baseline Assessment Procedures. [name] will coordinate the recruitment of the participants with the help of CHWs. We will recruit a total of 58 dyads (Table 1). Baseline visits will take place at local community centers using private rooms. Dyads will complete informed consent, height, weight and waist circumference assessments, as well as complete a computer-based survey. Randomization will follow a random-numbers table (families/staff unblinded). Standard-Care. Families randomized to this group will receive FC-workbook. No additional materials or intervention contact will be provided. CHWs will follow a retention protocol to ensure these individuals return to 6-month assessments. Intervention Delivery. Families randomized to this group will receive the adapted version of the intervention described above. Drs. [name] and [name] will monitor IVR completion reports and assist the student-worker and CHWs in the on-going monitoring and engagement of participants during the intervention. Measurements and Data Collection. All measures (see table at PHS section for description) will be collected prior to intervention initiation and at 6 months post baseline (Figure 3). Weight will be assessed using a digital scale calibrated for accuracy prior to each assessment period using standard weights of a known quantity (e.g., 100-pound dumbbell). Height will be measured with a stadiometer, calibrated in 0.1-cm intervals. Waist circumference will be measured with a spring-loaded cloth tape measure at the level of the iliac crest using the average of the two closest measurements. Other Measures. Children and parents will complete measures of physical activity^{98,99}, eating behaviors¹⁰⁰, beverage intake¹⁰¹, quality of life^{102,103} acculturation^{104,105}, and health literacy¹⁰⁶. Parents will also complete home environment¹⁰⁷ surveys. During the 6-month assessment parents will complete program satisfaction surveys and a short exit interview with a CHW. Feasibility will be assessed according to intervention relevant factors (RE-AIM dimensions, engagement, attendance and completion rates), cost-effectiveness, cultural

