Effectiveness	
 -Primary outcome (BMI z-score) and secondary clinical and self-management outcomes (Table 2) by control/IVR -Comparison of outcomes in subjects who withdraw vs. complete intervention - Staff and leaderships perceptions about delivering FBCO program via IVR and group sessions 	
 -Recruitment/enrollment/subject tracking logs (including completion, dropout and loss to follow-up rates/reasons) [CHWs] -Clinical data forms and surveys at 0,6 months [SW, CHWs] -Qualitative interviews with staff and leadership [[name] , PI [name]] 	
 Selected constructs will include: Facilitation: IVR and group based sessions and workbook facilitation strategies; Innovation: adaptation to deliver strategies to L/Hs in the context of rural NE
Adoption	
 - Staff and leaderships perceptions about delivering FBCO program via IVR and group sessions 	
 -Qualitative interviews with staff and leadership [[name] , PI [name]] 	Recipients : perceptions of participants (Beneficiaries), and staff (Recipients)
Implementation	
 - IVR completion reports; group session attendance and observation reports; proportion of content delivered as intended (fidelity) - Changes made during the implementation process (adaptation) tracked by the FRAME - Number of Calls completed and contact hours - Participant satisfaction - Qualitative feedback on barriers/facilitators from L/Hs/staff using i-PARIHS constructs 	
 -IVR completion forms (IVR System) [[name]] -IVR logged call duration (IVR System) [[name]] - Participant Satisfaction survey [SW, CHWs] -Qualitative interviews with participants, staff [[name] , PI [name]] 	Context : documentation of the capacity (human and financial resources); assessment of support from the leadership at the state and local levels

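### Gender differences in the primary outcome are explored by separate within-gender Fisher tests, with no planned estimate or interval for the treatment-by-gender contrast

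*Combined protocol and SAP*

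**What the plan says.** Section 12.B (Statistical Analysis, Specific Aim 2) takes as primary outcome the share of children whose BMI z-score falls, tested by chi-square with Fisher's exact test as fallback. On effect size it says: "The degree of association will be summarized using the odds ratio". It continues: "Potential gender, and acculturation scores (external and familial language use, and social relations) differences will be explored via stratification". The method named for gender is: "Comparisons between groups within gender will be done using Fishers exact test". The paragraph ends with a significance level of 0.05.

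Section 12.E (Statistical Analysis) gives a mixed model for BMI z-score, introduced by "In its simplest form, the model generally can be shown as". It has one treatment term: "Relative treatment effect between conditions will be captured by coefficient" theta. No treatment-by-gender term is named, and participant-level covariates are left unspecified. Table 1 in 12.E lists the effectiveness measure as "Primary outcome (BMI z-score) and secondary clinical and self-management outcomes", so the outcome appears in a continuous form there.

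On size, Section 12.B (Sample Size Calculation) needs 23 dyads per group and says: "To account for a 25% attrition rate at 6-month we will recruit a total of 58 (29 per group) dyads".

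**The concern.** The question is whether the FC effect differs between boys and girls. That calls for an estimate of the difference between two effects. The plan instead supplies two separate tests, each asking whether there is an effect in one gender. One p-value below 0.05 and one above it can easily arise from the same true effect in both groups, especially when each group is small.

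Section 12.B says feasibility findings will inform whether the intervention goes on to further testing. A boys-only or girls-only result, read as a real difference, could shape that next study. Two non-significant results could equally be misread as showing that gender does not matter.

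**Working it through.** **The plan's own figure.** With difference 0.05 and SD 0.06 (Section 4; Section 12.E Sample Size Calculation), two-sided alpha 0.05 and 80% power:

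n per group = 2 × (0.06 × (1.960 + 0.842) / 0.05)² = 22.6, rounded up to 23. This reproduces the plan's 23.

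**Children per arm per gender.** Half of 23 is 11.5, and half of 29 × 0.75 = 21.75 is 10.9, so I use 11. Half of 29 is 14.5, so I use 14 for almost no dropout. The equal gender split is an assumption.

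**Share reducing BMI z-score.** Assuming normal changes, P(reduce) = Φ(-mean change / 0.06). The documents do not give the SC mean change, so I use +0.03, 0 and -0.03.

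| SC mean change | SC | FC, effect 0.05 | FC, effect 0.10 |
|---|---|---|---|
| +0.03 | 30.9% | 63.1% | 87.8% |
| 0 | 50.0% | 79.8% | 95.2% |
| -0.03 | 69.1% | 90.9% | 98.5% |

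**Within-gender Fisher test.** Exact enumeration of both binomials, two-sided, p ≤ 0.05. Sidedness is not stated in the plan. Each cell gives SC mean change +0.03 / 0 / -0.03.

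| | 11 per arm per gender | 14 per arm per gender |
|---|---|---|
| Power, effect 0.05 | 19 / 17 / 9% | 25 / 26 / 17% |
| Power, effect 0.10 | 69 / 52 / 20% | 83 / 72 / 38% |
| Rejection, no effect | 1.5 / 1.7 / 1.5% | 2.1 / 1.7 / 2.1% |

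**Exactly one gender significant.** If the rejection probabilities are a and b, this is a(1 - b) + b(1 - a). For 11 per arm per gender and SC mean 0, identical effects give 2 × 0.165 × 0.835 = 0.276.

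| True effects in the two genders | 11 per arm per gender | 14 per arm per gender |
|---|---|---|
| 0.05 and 0.05 (identical) | 31 / 28 / 17% | 37 / 38 / 28% |
| 0.05 and 0 | 20 / 18 / 10% | 26 / 26 / 18% |
| 0.10 and 0 | 68 / 52 / 21% | 82 / 71 / 38% |

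The second row halves the average effect to 0.025. The third keeps it at 0.05. Compared with identical effects, the pattern is rarer in every cell of the second row and commoner in every cell of the third.

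**What a direct contrast would deliver.** For the log ratio of odds ratios with n per arm per gender, SE = √(2 × [1/(n p₁(1-p₁)) + 1/(n p₂(1-p₂))]). At n = 11, p₁ = 0.50 and p₂ = 0.798, SE = √(2 × [0.364 + 0.564]) = 1.36. The 95% CI is then the estimate multiplied or divided by exp(1.96 × 1.36), about 14.

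With a Firth-penalised model, the median CI factor under identical effects is 12 / 15 / 66 at 11 and 9 / 11 / 21 at 14. Its penalised likelihood-ratio test at 0.05 flags 2-4% of trials when effects are identical and 11-21% when they are 0.05 and 0.

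**Sparse cells.** At least one of the four gender-by-arm groups has all or none reducing in 5 / 16 / 59% of trials at 11 and 1 / 8 / 46% at 14. An ordinary logistic interaction then has no finite estimate.

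**The case against.** The strongest reply is that this is labelled exploration in a feasibility study. No hypothesis concerns gender, the primary test is untouched, and the plan sets no rule for reading the two p-values. The harm therefore needs a misreading that the documents do not commit to. All of this stands and limits the point to an exploratory-analysis correction. It does not rescue the method, because the plan still attaches a test and a 0.05 level to a comparison that does not answer the stated question.

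A second reply is that stratum odds ratios may be reported and that the Section 12.E model is shown only in its simplest form. That is fair: neither rules out a contrast. But none is planned, and two stratum odds ratios carry no interval for their ratio.

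A third is that the replacement has little power. That also stands, but a very wide interval shows the reader how little is known, which discordant p-values do not.

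A reader might infer more than the documents support:

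- **That the p-values point the wrong way**, with one-gender significance a sign of equal effects. This holds for 0.05 against 0 but reverses for 0.10 against 0, and nothing in the documents favours either scenario.
- **That two tests inflate false positives.** The nominal figure is 1 - 0.95² = 9.75%, but Fisher's conservatism brings it to about 3.0-4.5% at these sizes.
- **That acculturation has the same fault.** Section 12.B names the within-stratum Fisher test for gender and no such test for the child acculturation scores.

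**Conclusion.** The point holds for gender. The planned within-gender Fisher tests do not assess whether the effect differs, and no contrast or interval is planned in Section 12.B or 12.E. At the plan's size, 17-38% of trials with identical effects would show significance in one gender only. That pattern is not a reliable sign of a gender difference, because its frequency under a true difference runs from 10% to 82% across the scenarios examined.

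The figures rest on the plan's difference of 0.05 and SD of 0.06, and on my assumptions of normal changes, an equal gender split, two-sided tests and SC mean changes from +0.03 to -0.03. That separate p-values do not test a difference depends on none of these. The correction is worth making but concerns interpretation of an exploratory analysis only.

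**What to change.** In Section 12.B, replace the within-gender significance tests with an exploratory treatment-by-gender ratio of odds ratios and its 95% CI, from a logistic model of the planned binary outcome. Use a sparse-data method, because all-or-none groups can occur often. Firth penalisation with profile-likelihood intervals is a reasonable choice, not the only one. Show gender-specific odds ratios with CIs and no stratum p-values. State that the results are descriptive and support no claim either of difference or of consistency between genders.

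If the sponsor keeps continuous BMI z-score as the primary outcome (Section 12.E, Table 1 and model), add the same treatment-by-gender term to that model.

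The cost is a few lines of analysis-plan wording and minor programming, with no new data and no change to the primary test. The drawback is imprecision: about 11-21% power for an effect of 0.05 in one gender and none in the other, and a CI reaching a factor of roughly 9 or more either way.
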